6.7.4. Concomitant Medications and Non-drug Treatments

Prior drug and non-drug treatment, concomitant drug and non-drug treatment will be summarized according to CaPS.

6.8. Safety Summaries and Analyses

Safety analyses will be based on the SAF analysis set.

All clinical AEs, SAEs, TEAEs, withdrawal due to AEs, ECGs, vital signs and safety laboratory data will be reviewed and summarized on an ongoing basis during the study to evaluate the safety of subjects.

Safety data will be presented in tabular and/or graphical format and summarized descriptively, where appropriate. All safety endpoints will be listed and summarized in accordance with CaPS. Categorical outcomes (eg, AEs) will be summarized by subject counts and percentage. Continuous outcome (eg, blood pressure, pulse rate, etc.) will be summarized using N, mean, median, standard deviation, etc. Change from baseline in laboratory data, ECGs and vital signs will also be summarized. Subject listings will be produced for these safety endpoints accordingly.

6.8.1. Adverse Events

The safety data will be summarized in accordance with CaPS. All safety data will be summarized descriptively through appropriate data tabulations, descriptive statistics, categorical summaries, and graphical presentations. Safety endpoints for the study include:

- Treatment-emergent AEs and SAEs;
- Withdrawals from active treatment due to AEs;
- Serious infections, defined as any infection (viral, bacterial, and fungal) requiring hospitalization or parenteral antimicrobials.

AEs will be displayed by MedDRA system organ class (SOC).

It should be recognized that most studies are not designed to reliably demonstrate a causal relationship between the use of a pharmaceutical product and an adverse event or a group of adverse events. Except for select events in unique situations, studies do not employ formal adjudication procedures for the purpose of event classification. C CI

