2.3. Benefit/Risk Assessment

There was clinically meaningful benefit demonstrated for abrocitinib 200 mg QD and 100 mg QD in the Phase 2b POC study in adult participants with moderate-to-severe AD. The potential risks of treatment include those that were noted in Phase 2b and/or those based on the known pharmacology of other well studied JAK inhibitors (such as tofacitinib) and include viral reactivation, serious and opportunistic infections, hematopoietic effects (including decreases in platelet counts), malignancy and immunoproliferative disorders.

Overall, there is a favorable benefit-risk profile to support the continued development into Phase 3 of abrocitinib for the treatment of participants with AD.

More detailed information about the known and expected benefits and risks and reasonably expected adverse events of abrocitinib is provided in the IB, which is the single reference safety document (SRSD) for this study.

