
f. Other situations:
 
• Medical or scientific judgment should be exercised in deciding whether SAE reporting is appropriate in other situations such as important medical events that may not be immediately life-threatening or result in death or hospitalization but may jeopardize the participant or may require medical or surgical intervention to prevent one of the other outcomes listed in the above definition. These events should usually be considered serious.• Examples of such events include invasive or malignant cancers, intensive treatment in an emergency room or at home for allergic bronchospasm, blood dyscrasias or convulsions that do not result in hospitalization, or development of drug dependency or drug abuse.• Suspected transmission via a Pfizer product of an infectious agent, pathogenic or non-pathogenic, is considered serious. The event may be suspected from clinical symptoms or laboratory findings indicating an infection in a patient exposed to a Pfizer product. The terms "suspected transmission" and "transmission" are considered synonymous. These cases are considered unexpected and handled as serious expedited cases by pharmacovigilance personnel. Such cases are also considered for reporting as product defects, if appropriate.

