10.10. Appendix 10: Monitoring and Discontinuation Criteria

Monitoring Criteria

The following laboratory abnormalities require prompt retesting:

- Neutrophil counts <1000 neutrophils/mm³; confirmed promptly by repeat testing, ideally within 3-5 days;
- Platelet counts $<75,000$ platelets/mm³; confirmed promptly by repeat testing, ideally within 3-5 days;
- Any single hemoglobin value <9.0 g/dL or one that drops ≥ 2 g/dL below baseline; confirmed promptly by repeat testing, ideally within 3-5 days;
- Any single AST and/or ALT elevation >3 times the upper limit of normal regardless of accompanying symptoms or the total bilirubin should prompt repeat testing. This should also prompt review of [Appendix 6](#) (Liver Safety); additional investigations must be conducted.

Temporary Interruption to Dosing

Temporary interruption to dosing is not allowed in this study, except when specified in the protocol for participant safety.

Discontinuation Criteria

Participants must be permanently discontinued from treatment if they meet any of the following criteria at any point in the study:

- Marked prolongation of the QTcF interval to >500 ms or >60 ms change from screening ECG.
- Serious infection (see definition for Serious Adverse Events in Section [10.3.2](#)) must result in temporary interruption of study intervention. Study intervention cannot be restarted until the serious infection has resolved, and this has been discussed and agreed with the Pfizer medical monitor. If the participant cannot be restarted on study intervention within 21 days, or the infection is not resolved, or there is no agreement received from the Pfizer medical monitor to restart study intervention then the participant must be permanently discontinued from study intervention.
- Any bleeding event thought to be associated with a platelet count reduction per the judgement of the investigator (or, if necessary/desired, following discussion with sponsor).
- Adverse event, per judgment of the investigator, requiring discontinuation from treatment (or, if necessary/desired, following discussion with sponsor).

NOTE: any initial lab value below must be retested within 48 hours.

- Two sequential platelet counts $<50,000/\text{mm}^3$. If the participant has a platelet count $<25,000/\text{mm}^3$, study intervention should be temporarily withheld pending the confirmatory retest.
- Two sequential neutrophil counts $<500/\text{mm}^3$.
- Two sequential lymphocyte counts $<500/\text{mm}^3$.

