2. INTRODUCTION

This SAP provides the detailed methodology for summary and statistical analyses of the data collected in Study B7451037. This document may modify the plans outlined in the protocol; however, any major modifications of the primary endpoint definition or its analysis will also be reflected in a protocol amendment.

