3.5. Safety Endpoints

Safety will be assessed by the spontaneous reporting of AEs, physical examinations, and clinical laboratory results in all subjects who receive at least one dose of the investigational product. Unscheduled safety assessments may be performed at any time during the study to assess any perceived safety concerns. Endpoints will be assessed as:

- Incidence of treatment emergent adverse events (AEs) and serious AEs (SAEs).
- AEs leading to discontinuation.
- Serious infections, defined as any infection (viral, bacterial, and fungal) requiring hospitalization or parenteral antimicrobials or met other criteria that required the event be classified as serious;
- Incidence of clinical abnormalities and change from baseline in selected clinical laboratory values, ECG measurements, and vital signs.

The safety endpoints will be defined in accordance with Clinical Data Interchange Standards Consortium (CDISC) aligned Pfizer Standards (CaPS).

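### SAP 6.8.1 omits one of the three criteria for serious infection that SAP 3.5 and protocol 9.4.3 include, so a table built from it could under-count the endpoint

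*SAP*

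**What the plan says.** Serious infection is defined for analysis in three places.

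- **SAP 6.8.1 (Adverse Events)**, in the part of the SAP that sets out analyses and summaries: "Serious infections, defined as any infection (viral, bacterial, and fungal) requiring hospitalization or parenteral antimicrobials". The sentence ends there, and no redaction falls inside it.
- **SAP 3.5 (Safety Endpoints)**, in the part of the SAP that defines endpoints, covers infections "requiring hospitalization or parenteral antimicrobials or met other criteria that required the event be classified as serious".
- **Protocol 9.4.3 (Safety Analyses)** uses the same three criteria as SAP 3.5.

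A fourth place uses the term for handling study treatment. Protocol Appendix 10 writes "Serious infection (see definition for Serious Adverse Events in Section" and points to protocol 10.3.2. That section covers death, life-threatening events, hospitalization, persistent disability and congenital anomaly, and also "important medical events that may not be immediately life-threatening or result in death or hospitalization".

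**The concern.** An infection can be a serious adverse event without a hospital stay or a parenteral drug. An example is one judged an important medical event and treated with oral drugs as an outpatient. Under SAP 3.5 and protocol 9.4.3 that participant belongs in the serious-infection count. Under SAP 6.8.1 as written, the participant does not.

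Infection is a recognised concern for this drug class. Protocol 2.3 says that the potential risks "include viral reactivation, serious and opportunistic infections, hematopoietic effects". With two definitions in the SAP, two programmers could each follow it faithfully and produce different serious-infection lines. If the difference surfaced only after unblinding, someone would have to choose a definition with the data in view, and one of the two can only give the lower count.

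**Working it through.** There is no sample size, power or event figure to reproduce. The check compares texts and applies set inclusion.

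**Step 1. Code the criteria.** For an infection, let A = required hospitalization, B = required parenteral antimicrobials, and C = met another criterion that made the event serious.

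| Place | Counts an infection if |
|---|---|
| Protocol 9.4.3 | A or B or C |
| SAP 3.5 | A or B or C |
| SAP 6.8.1 | A or B |
| Protocol Appendix 10 (treatment handling) | it meets the SAE definition, which includes C |

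Appendix 10 is not identical to the first two rows, because the SAE definition does not name parenteral antimicrobials as a criterion of its own. It does share the feature at issue: the other seriousness criteria are included. Only SAP 6.8.1 leaves them out.

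**Step 2. Direction.** Every infection satisfying (A or B) also satisfies (A or B or C). So count(6.8.1) ≤ count(3.5), with no exception.

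**Step 3. Shortfall.** count(3.5) − count(6.8.1) = the number of participants whose only qualifying infections meet C but neither A nor B. The documents give no rate for such infections, so the difference cannot be sized. It may be zero.

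**Step 4. Was the narrowing deliberate?** SAP Section 2 says "This document may modify the plans outlined in the protocol". That could excuse a departure from protocol 9.4.3, but not a conflict with SAP 3.5. The table of changes in SAP Section 1 records no change to this definition and no reason for one. An incomplete copy is the likeliest explanation.

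**Step 5. Where would an omitted case still appear?** A case that meets C is by construction a serious adverse event. SAP 6.8.1 also lists "Treatment-emergent AEs and SAEs" and displays adverse events by system organ class, and SAP 6.8 provides subject listings. The case would be absent from the serious-infection line but present elsewhere in the report.

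**The case against.** The strongest reply is that SAP 3.5 defines the endpoint and 6.8.1 merely restates it in short form. SAP Section 3 is the section for definitions. Both 3.5 and 6.8.1 also refer to the sponsor's data standards (CaPS), which are not among the documents. So nothing shows that the table would be programmed from 6.8.1. This stands, and it is why the under-count is a possibility rather than a prediction. It does not remove the conflict: 6.8.1 states a complete definition, sits in the section a table programmer would naturally consult, and does not refer back to 3.5.

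A reader might infer more than the documents support, in three ways.

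- *That the endpoint will be under-counted.* This needs two conditions: programming from 6.8.1, and at least one infection serious only on another criterion. Neither is established.
- *That the error is worth 5.9 percentage points per arm.* With 17 planned per arm, one participant is 1/17 = 5.9 points. But any single event has that effect in an arm of 17, so the figure says nothing about how many cases the wording would lose.
- *That a key safety endpoint is affected.* Serious infection is a listed safety endpoint in protocol 9.4.3 and SAP 3.5. It has no line of its own in the objectives tables (protocol Section 3, SAP Table 2), and protocol 8.3.8 marks adverse events of special interest as not applicable. The analysis is descriptive.

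It is also fair to say that handling of individual participants does not depend on 6.8.1. Appendix 10 uses the SAE definition, and protocol 10.1.5 sends opportunistic infections to blinded adjudication under separate charters.

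**Conclusion.** The inconsistency is certain. SAP 6.8.1 is narrower than both SAP 3.5 and protocol 9.4.3, and no redaction, recorded change or licence to modify the protocol accounts for it. The direction is also certain: following 6.8.1 can lower the count or leave it unchanged, never raise it.

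The consequence is conditional and probably small. It depends on which section or standard the programmer follows and on whether any infection is serious only on another criterion. The documents settle neither. At worst, one descriptive line omits cases that the overall SAE summary and the listings still show. The primary analysis is not touched. This is a modest defect in the specification of a safety endpoint, worth correcting because the correction is simple and the endpoint should have a single definition before treatment codes are opened.

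**What to change.** Before unblinding, replace the serious-infection wording in SAP 6.8.1 with the full definition from SAP 3.5 and protocol 9.4.3, or delete the wording there and refer to SAP 3.5. Confirm that the table specification uses the same three criteria.

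The cost is one clause in the SAP and a check of the programming specification. No new data, protocol amendment or change to participant handling is needed. The reported count may be higher than under the present 6.8.1 wording if any such infection occurs; it cannot be lower.

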6.8.2. Laboratory Data

Laboratory data will be listed and summarized in accordance with the CaPS reporting standards. Summaries of subjects meeting pre-specified monitoring and discontinuation criteria will be created using methods for categorical data.

6.8.3. Vital Signs

Vital signs will be summarized at baseline, Weeks 2, 4, 8, and 12/End of Treatment visits. Height and weight will be summarized at baseline (both) and End of Treatment (weight only) visits.

6.8.4. Electrocardiogram

ECG parameters, if applicable, will be summarized at baseline

6.8.5. Physical Examination

Physical examinations will be summarized at baseline and all-available post-baseline visits.

The C-SSRS will also be collected and reported using descriptive summaries for recent history/baseline and post-baseline visits.

7. INTERIM ANALYSES

After the first 15 participants have completed the trial, there will be an interim analysis to examine platelet values. A longitudinal analysis will be conducted to determine if there is a change from baseline in platelet values. The data will remain blinded so that no one will know the participants' assigned treatment and thus the analysis will not look for any treatment differences. Correlation analyses may also be conducted to look for potential relationships between platelet values and other laboratory measures, such as TPO. There will not be any decision rules associated with this interim analysis, so there will be no changes to the conduct or continuation of the trial based on these analyses.

There will be a program-level E-DMC (see below) who will periodically review the safety data from the study.

This study will use an E-DMC. The E-DMC is independent of the study team and includes only external members. The E-DMC will be responsible for ongoing monitoring of the safety of participants in the study according to the charter.

The recommendations made by the E-DMC to alter the conduct of the study will be forwarded to Pfizer for final decision. Pfizer will forward such decisions, which may include summaries of aggregate analyses of endpoint events and of safety data that are not endpoints, to regulatory authorities, as appropriate. Composition of the E-DMC and processes under which the E-DMC operates will be documented in the E-DMC charter.

9. APPENDICES

Appendix 1. Summary of Clinical Efficacy Analyses

Efficacy Endpoints	Population	Analysis Method	Missing Data Imputation	Primary Analysis for Co-primary
Week 12 IGA Response	FAS	CMH	NR	Yes
	PPAS	CMH	NR	No
Week 12 EASI-75 Response	FAS	CMH	NR	Yes
	PPAS	CMH	NR	No
Weeks 2, 4, 8 and 12 NRS4 for severity Response	FAS	CMH	NR+MI	
	PPAS	CMH	NR+MI	
	FAS	CMH	NR	
Time to NRS4 for severity	FAS	Kaplan-Meier	OD	
Weeks 2, 4 and 8 IGA Response	FAS	CMH	NR	
Weeks 2, 4, 8 and 12 EASI-50 / EASI-90 / EASI-100 Response	FAS	CMH	NR	
Weeks 2, 4 and 8 EASI-75 Response	FAS	CMH	NR	
Weeks 2, 4, 8 and 12 CFBL in Total EASI Score	FAS	MMRM	OD	
Weeks 2, 4, 8 and 12 CFBL in NRS for severity	FAS	MMRM	OD	
Weeks 2, 4, 8 and 12 CFBL in %BSA	FAS	MMRM	OD	

CFBL=Change from baseline; CMH=Cochran-Mantel-Haenszel; ANCOVA=Analysis of Covariance; MMRM=Mixed-effect Model Repeated Measures; NR=Non-Responder; OD=Observed Data; MI=Multiple Imputation.

Appendix 2. Definition and Use of Visit Windows in Reporting

Visit windows will be used for efficacy variables, and for any safety data that display or summarize by study visit. For other endpoints (eg, ECG, vital signs), visit windows will be applied for summary statistics by study visits if required.

Visit Label	Target Day	Definition [Day window]
Screening		Days -28 to Day -1
Baseline	Day 1 (Day of first dose)	Last observation prior to and including day of first dose
Week 2	15	Days 2 to 22
Week 4	29	Days 23 to 36
Week 6	43	Days 37 to 50
Week 8	57	Days 51 to 71
Week 12	85	Days 72 to 99
Follow Up/End of Study		
Week 16	-	Days 100 to -

For the lab values, if the calculated study day for the labelled baseline visit is not study Day 1, but falls within 28 days before the start of the study dosing, then that data should be used for the baseline instead of leaving baseline missing.

For the other values, if the calculated study day for the labelled baseline visit is not study Day 1, but falls before the start of the study dosing, then that data should be used for the baseline instead of leaving baseline missing.

If two or more visits fall into the same window, keep the one closest to the Target Day. If two visits are equaled distant from the Target Day in absolute value, the later visit should be used.

Safety analysis may follow CaPS standards.

CCI

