8.1.7.1. Body Surface Area – Efficacy (BSA Efficacy)

BSA Efficacy will be derived from the sum of the BSA in handprints across 4 body regions assessed as part of the EASI assessment ([Table 4](#)). Handprint refers to that of each individual participant for their own measurement. The BSA Efficacy ranges from 0 to 100%, with higher values representing greater severity of AD. Assessments will be collected at various time points as described in the [Schedule of Activities](#).

CCI

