6. ANALYSES AND SUMMARIES

Point estimates and 95% confidence intervals will be provided for each of the PF-04965842 QD treated groups (200 mg and 100 mg) and placebo.

A summary of analyses for clinical efficacy endpoints is provided in Appendix 1. Visit windows to be used for all efficacy analyses and some relevant safety analyses are detailed in Appendix 2.

Data collected at Week 16 will be displayed in listings only, and will not be part of any analyses, unless specifically noted otherwise.

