6.3.4. Change from Baseline in BSA%

- Summary: Change from baseline at all scheduled visits;
- Population: FAS;
- Statistical Method: Descriptive (LSmean, SD, mean difference, SE, 95% CI, median, Q1, Q3);
- Missing Data: Observed Data.

CCI [REDACTED]
[REDACTED]
[REDACTED]
[REDACTED]
[REDACTED]
[REDACTED]
[REDACTED]

C

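### Read literally, SAP Appendix 2 labels an early discontinuer's off-drug Visit 11 as Week 4 to Week 12, at odds with the Week 16 listings-only rule, and folds Day 4 hematology into Week 2

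*SAP*

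**What the plan says.** SAP Section 6 makes the windows general for efficacy: "Visit windows to be used for all efficacy analyses and some relevant safety analyses are detailed in Appendix 2". Appendix 2 repeats the scope: "Visit windows will be used for efficacy variables, and for any safety data that display or summarize by study visit". Its table assigns each observation by study day counted from first dose:

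- Week 2: Days 2 to 22 (target 15)
- Week 4: Days 23 to 36 (target 29)
- Week 6: Days 37 to 50 (target 43)
- Week 8: Days 51 to 71 (target 57)
- Week 12: Days 72 to 99 (target 85)
- Week 16, grouped under follow-up/end of study: Day 100 onward

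No row refers to last dose. Competing visits are resolved thus: "If two or more visits fall into the same window, keep the one closest to the Target Day"; a tie goes to the later visit.

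Section 6 also says "Data collected at Week 16 will be displayed in listings only, and will not be part of any analyses", unless specifically noted otherwise. Both Schedules of Activities head the Visit 11 column Week 16 (EOS), and both note that for early terminators Visit 11 takes place 4 weeks after last dose. Protocol Appendix 10 gives the sequence after a discontinuation criterion is met: end-of-treatment visit, then the 4-week follow-up period.

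For %BSA, protocol 8.1.7.1 derives the value from handprints "assessed as part of the EASI assessment", and EASI is scheduled at Visit 11. SAP 6.3.4 summarizes the change from baseline with "Missing Data: Observed Data".

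For laboratory data, the protocol schedule marks hematology on Day 4, and the protocol synopsis says platelet and RBC counts are to be analyzed at every scheduled time point. SAP 6.8.2 says "Laboratory data will be listed and summarized in accordance with the CaPS reporting standards", and Appendix 2 ends with "Safety analysis may follow CaPS standards".

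**The concern.** Two participants at the same point, 4 weeks off drug, can be handled differently because of the calendar. The completer who does not enter the extension has Visit 11 at about Day 113, labelled Week 16 and only listed. The participant who stopped on Day 57 has Visit 11 on Day 85, exactly the Week 12 target. Under Appendix 2 that off-drug value enters the Week 12 mean beside participants still on treatment, and nothing in the table shows it.

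If Section 6 means nominal Visit 11 when it says Week 16, that visit should be listed only. Section 6 and Appendix 2 then disagree about the same observation, and a programmer has to choose between them.

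The Day 4 question is separate and conditional. A hematology sample scheduled in its own right has no row of its own in Appendix 2. Any by-visit table built on these windows would not show it as a time point.

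**Working it through.** **Check on the windows.** The midpoints of adjacent target days 15, 29, 43, 57, 85 and the scheduled Day 113 are 22, 36, 50, 71 and 99. These equal the stated upper limits, so the table follows a midpoint convention.

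**Visit 11.** Let L be the last-dose day, 1 to 84. Visit 11 falls on Day L + 28. Placing that day in the Appendix 2 table gives:

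| Last-dose day L | Visit 11 day | Label | Days of L |
|---|---|---|---|
| 1–8 | 29–36 | Week 4 | 8 |
| 9–22 | 37–50 | Week 6 | 14 |
| 23–43 | 51–71 | Week 8 | 21 |
| 44–71 | 72–99 | Week 12 | 28 |
| 72–84 | 100–112 | Week 16 | 13 |

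Weeks 4, 8 and 12 together: 8 + 21 + 28 = 57 of 84 days (67.9%). Another 14 days give Week 6, where no EASI is scheduled. With the ±3-day window the visit falls between L + 25 and L + 31. The count then runs from 60 to 54, and the last affected last-dose day runs from 74 to 68. A completer's Visit 11 is on Day 110 at the earliest, so it is always Week 16.

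**Does the keep-closest rule remove it?** Suppose the end-of-treatment visit is on Day L + g. The documents do not state g, so 0 to 7 days is an assumption.

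- g = 0: the two visits are 28 days apart and never share a window. All 57 days stand.
- g = 1: they share Week 12 only for L = 71 (Day 72, 13 days from target; Day 99, 14 days). End-of-treatment is kept, which leaves 56.
- g = 2: L = 70 is a 13-day tie, so the later visit, Visit 11, is kept; L = 71 keeps end-of-treatment. 56 remain.
- g = 7: they share Week 12 for L = 65 to 71. Visit 11 is kept for 65 to 67 and end-of-treatment for 68 to 71. 53 remain.

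So Visit 11 still stands at Week 4, 8 or 12 on 53 to 57 of 84 days (63% to 68%).

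**Which outputs are exposed.**

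- *%BSA change:* exposed. It is collected with EASI, EASI is scheduled at Visit 11, the windows cover all efficacy analyses, and 6.3.4 uses observed data with no off-treatment exclusion.
- *EASI change:* exposed only if the row in SAP Appendix 1 is run.
- *By-visit laboratory tables:* exposed only if these windows are used rather than CaPS.
- *Primary skin biomarkers:* not exposed, because no biopsy is scheduled at Visit 11.
- *Binary responses:* not exposed under SAP 5.1.1, which makes a participant a non-responder after stopping treatment.

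**Scale.** If an arm has 17 observed values and k of them are off-drug Visit 11 values, its mean moves by k/17 of the off-drug minus on-drug gap: 1/17 = 5.9%, 2/17 = 11.8%, 3/17 = 17.6%. The gap and k are unknown.

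**Day 4.** With its ±1-day window the sample falls on Days 3 to 5, inside Week 2, at 12 to 10 days from target 15. The Day 15 visit (±1) is 0 to 1 day away. Any later result up to Day 22 is nearer the target than a Day 3 to 5 result. The Day 4 result is therefore dropped when a Day 15 result exists and reported as Week 2 when it does not. Day 4 is 1 of 5 post-baseline on-treatment hematology time points (Days 4, 15, 29, 57, 85).

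**The case against.** The best defence is that the documents, read together, already give the answer. Appendix 2 groups Week 16 under follow-up, both schedules call Visit 11 Week 16, and Section 6 sends Week 16 to listings. That is a fair reading of intent, and it means the problem is two passages that do not fit rather than a settled wrong analysis. It does not remove the problem, because Appendix 2 applied as written still assigns the earlier label.

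Second, using post-discontinuation data at its actual study day is a legitimate choice, and no estimand is stated for %BSA. That is true in principle. But the listings-only rule indicates that the follow-up visit was meant to stay out of the analyses, and the SAP does not declare the opposite choice for %BSA.

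Third, laboratory data are to follow CaPS, which is not among the documents, and Appendix 2 permits it for safety. This stands, and it makes the Day 4 point conditional. The SAP's safety laboratory list (3.5.2) also omits lymphocyte subsets, so it is not shown that the windows reach them. Exploratory sections are redacted and may contain a Day 4 analysis. The CaPS allowance covers safety only, so it does not protect %BSA.

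Some stronger readings are tempting. A reader might infer that Day 4 results receive no label at all; they are labelled Week 2. A reader might infer that Day 4 data are lost to the trial; the visible text shows this only for tables built on these windows. A reader might take 68% as the chance of mislabelling; it counts calendar days, not participants.

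**Conclusion.** The Visit 11 point holds. For a last dose up to Day 71 (68 to 74 with the visit window), Appendix 2 as written gives the off-drug follow-up visit a Week 4, 6, 8 or 12 label, while a completer's same visit is listed only. The two SAP passages must be reconciled. The confirmed exposure is one descriptive output, the observed-data %BSA change summary.

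The consequence is low. SAP 5.1 plans no formal hypothesis tests. The effect needs a participant who both stops early enough and returns for Visit 11, and with no discontinuation rate the shift in any mean cannot be computed. The documents do not support a claim that the primary endpoint is affected. The protection of binary responses rests on the 5.1.1 rule; SAP 5.2.3 and 5.3 word it more narrowly, as withdrawal from the study.

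The Day 4 point holds only for by-visit hematology tables that use these windows. There it is at odds with the synopsis statement that platelet and RBC counts are analyzed at all scheduled time points.

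**What to change.** In SAP Appendix 2, state that the post-treatment follow-up visit (nominal Visit 11) is labelled Follow-up whatever its study day and falls under the Section 6 listings-only rule. Key this to the nominal visit, not to a general cut-off on days since last dose, so that end-of-treatment and Week 12 assessments and biopsies keep their labels.

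Where Appendix 2 windows are used for hematology (and for lymphocyte subsets, if they are windowed), add a Day 4 row covering Days 2 to 9 and start Week 2 at Day 10. This follows the existing convention: the midpoint of 4 and 15 is 9.5. Do not override CaPS; where it governs, confirm that it shows Day 4 as its own time point.

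As a clerical correction only, add the Day 4 mark to the hematology row of SAP Appendix 7, which has 7 marks against 8 in the protocol schedule.

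The cost is SAP wording and a programming rule, with no new data. The downside is slightly fewer observed values at Weeks 4, 8 and 12. The %BSA change summary (and EASI change, if run) would then exclude the follow-up visit, and the SAP should say so.
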